10.1.1.1 AE Severity Grading Criteria

The investigator will make an assessment of severity for each AE and SAE reported during the study and assign it to one of the following categories:

- **Mild**: No limitation in normal daily activity. Minor event requiring no specific medical intervention, asymptomatic laboratory findings only, marginal clinical relevance.
- **Moderate**: Some limitation in normal daily activity. Minimal intervention, local intervention, non-invasive intervention, transfusion, elective interventional radiological procedure, therapeutic endoscopy or operation.
- **Severe**: Unable to perform normal daily activity. Significant symptoms, which may require hospitalization or invasive intervention, elective interventional radiological procedure, therapeutic endoscopy or operation, life threatening or disabling events, events resulting in death.

Note: The terms serious and severe are NOT synonymous. The general term severe is often used to describe the intensity (severity) of a specific event. The event itself may be of relatively minor medical significance (e.g., severe headache). A severe headache does not necessarily need to be considered serious unless it meets the criteria of a serious adverse event.

10.1.1.2 AE Causality Assessment

The investigator will assess the relationship between the AE and the study treatment or the study procedure using a binary causality assessment. Causality will be reported separately for each study treatment received by the participant.

- **Related:** There is a reasonable possibility that the study treatment, study drug, or study protocol caused the event.
- **Not Related:** There is no reasonable possibility that the study treatment caused the event. There may be other plausible alternative causes for the event which may include but are not limited to: medical history, lack of efficacy, worsening of treated condition, other treatment, concomitant medications, withdrawal of study treatment, or erroneous administration of treatment.

10.1.2 Serious Adverse Events (SAE)

All SAEs that occur from the time of signed ICF through the study termination visit (+/- 2 days) should be reported. Any SAE that is continuing at the time of the study termination visit will be followed until the outcome of the event is known. Whenever possible the investigator should report the overall diagnosis of the event(s) rather than the signs and symptoms associated with the event(s). Treatment or intervention of an event should not be reported as an SAE. The event necessitating treatment or intervention should be reported.

10.1.2.1 SAE Definition

An SAE is defined as any untoward medical occurrence that, at any dose, meets one or more of the criteria listed:

MAPPUSX Protocol

Amendment 3 Version 1: 15 March 2023

- 1. Results in death.
- 2. Is life threatening.
- 3. Requires inpatient hospitalization or prolongation of an existing hospitalization.
- 4. Results in persistent or significant disability/incapacity.
- 5. Is a congenital anomaly or birth defect.
- 6. Is an important medical event (event does not result in death or is life threatening, but based on medical judgement may jeopardize the participant and may require medical or surgical intervention to prevent one of the outcomes listed above).

Life Threatening: is an event that in the view of the investigator places the participant at immediate risk of death from the event as it occurred (e.g., anaphylaxis, ventricular fibrillation, respiratory arrest). This does not include events which hypothetically might have caused death if it were more severe.

Hospitalization or Prolongation of Existing Hospitalization: An event that requires hospitalization or prolongation of an existing hospitalization. Hospitalization does not include the following: emergency room visit (< 24 hour) or same day surgeries (as outpatient/same day/ambulatory procedures, if the surgery was preplanned prior to entering the study). If during a preplanned hospitalization, an event occurs that was not part of the preplanned hospital admission (e.g., thromboembolic event), then the event prolonging the hospitalization and not the diagnosis or event associated with the preplanned hospitalization should be reported.

10.1.3 Adverse Events of Special Interest (AESI)

An adverse event of special interest (AESI) is a serious or non-serious event of scientific and medical concern specific to the study intervention. The event may require further investigation and depending on the nature of the event, submission to the FDA or other applicable regulatory authorities. For the purpose of this trial, AESIs have been predefined.

AESIs will be reported on the SAE/AESI report form within 24 hours of discovery. Any AESI that also meets the criteria of a SUSAR (suspected unexpected serious adverse reaction) will be emergently reported to FDA and other appropriate regulatory agencies, PIs, IRBs and IECs. AESIs will be followed until the outcome of the event is determined.

AESIs will include the following:

- Cardiac arrhythmias, or AEs that are indicative of QT interval prolongation, including (but not limited to) Torsade de pointes, sudden death, ventricular extrasystoles, ventricular tachycardia, ventricular fibrillation and flutter, palpitations, and non-postural syncope
- Cardiac disorders (e.g., acute MI, angina pectoris, ischemic chest pain)
- Drug diversion, drug abuse and drug accountability (e.g., accidental poisoning, behavioral
 addiction, dependence, drug abuser, drug diversion, overdose, intentional overdose, intentional
 product misuse, poisoning deliberate, prescribed overdose, substance abuser, euphoria-like
 response, hallucination dissociative state, psychosis, aggression, drug tolerance, habituation, drug
 withdrawal syndrome, substance related disorders)

- Central nervous system vascular disorders (e.g., ischemic central nervous system vascular)
- Seizures
- Hypertensive crisis

conditions)

• Suicide, suicidal behavior (e.g., intentional overdose, intentional self-injury, suicide attempt, suicide threat, suspected suicide, suspected suicide attempt), C-SSRS Suicidal Ideation score of 4 or 5, and/or suicidal ideation judged to be serious or severe in the opinion of the investigator

MAPPUSX Protocol

Amendment 3 Version 1: 15 March 2023

10.1.4 Other Reportable Information

Other reportable AEs include but are not limited to the following:

- Any clinically significant worsening of a pre-existing condition
- An AE occurring from an overdose (i.e., a dose higher than that indicated in the protocol) of study drug whether accidental or intentional
- An AE occurring from abuse (e.g., use for nonclinical reasons of a study medication)
- An AE that has been associated with the discontinuation of the use of a study medication
- A medication error such as an inadvertent or accidental exposure with or without an AE

Any event meeting the abovementioned listing should be reported on an SAE/AESI report form and sent to the sponsor or designee within 24 hours of discovery. These events should be followed until the events have subsided, returned to baseline or in the case of permanent impairment, until the condition stabilizes.

10.1.5 SAE and AESI Reporting

In the event of an SAE or AESI, the investigator must fill in the SAE/AESI Report form. The form should be signed and dated. The SAE form should be sent to the sponsor or designee within 24 hours of awareness of the event. Each event should have a separate SAE/AESI form.

The investigator should include the minimum reportable criteria on the SAE/AESI report form. The minimum criteria include: a product, a participant, a reportable event, and a site/investigator. If any of the reportable criteria are missing, the Principal Investigator (PI) should acquire the information prior to submitting the SAE/AESI form.

It is not necessary to send source documentation to the sponsor as part of the SAE/AESI reporting function but the documentation should be available on site. However, the sponsor may request source documentation associated with the event (e.g., hospital admission, relevant tests, and labs, discharge summary, autopsy report) and the site should be able to supply the documentation when requested.

If source documentation is requested, all source documentation must be de-identified, redacted, or pseudonymized in all attached documents before being sent to the sponsor or designee. Any follow-up information should be provided on a new SAE/AESI report form with a sequential follow-up number starting with follow-up #1. The SAE/AESI report form should be used for any changes, revisions or additional report to the event.

The sponsor assumes responsibility for appropriate reporting of any suspected unexpected serious adverse reaction (SUSAR) to the regulatory authorities and governing bodies according to the local regulations.

The investigator (or sponsor where required) must report these events to the appropriate Institutional Review Board (IRB) and/or IEC (Independent Ethics Committee) that approved the protocol unless otherwise required and documented by the IRB/IEC.

All SAEs and AESIs should be followed until resolved, returned to baseline or stabilized to a level satisfactory to the investigator.

10.1.6 Pregnancy Reporting

- Details of all pregnancies in participants and their partners will be collected after the start of study intervention and until the participant's final visit.
- If a pregnancy is reported, the investigator will record pregnancy information on the appropriate form and submit it to the sponsor within 24 hours of learning of the pregnancy.
- Pregnancies should be reported on a pregnancy form.
- Pregnancies will not be considered SAEs. However, any pregnancy that meets the criterial of an SAE (e.g., still birth, spontaneous abortion) should be reported on both a pregnancy and SAE/AESI report form. The SAE form is due to the sponsor or designee within 24 hours of awareness of the event.
- Pregnancies will be followed until the outcome of the pregnancy is known.
- Live births will be followed for 30 days after delivery.

Any participant who becomes pregnant while participating in the study will not undergo any additional MDMA-assisted therapy sessions, though in some cases may continue participation in non-drug therapy sessions. Prior to continuation of non-drug study interventions following pregnancy, the following must occur:

- The sponsor and the relevant IRB/IEC give written approval.
- The participant and/or their partner gives signed informed consent.
- The investigator agrees to monitor the outcome of the pregnancy and the status of the participant and/or their partner and their offspring.

10.1.7 Participant Discontinuation or Withdrawal from Study

Reasons why a participant may discontinue or be withdrawn from the study may include but are not limited to:

- Development of toxicity which in the investigator's judgment precludes further therapy
- Participants request
- Participant non-compliance
- Intercurrent illness
- At the discretion of the investigator
- Pregnancy
- Study termination by the sponsor
- Protocol violation

When a participant is withdrawn, the investigator will notify the sponsor and clearly document in the medical record and appropriate case report form the reason for withdrawal from study. When possible, the investigator will perform the procedures indicated for the final visits within 30 days after the last medication dose.

10.2 Other Significant Events

Significant life events that may occur during the course of the study, including death of a loved one, loss of employment, or other hardship, may have an impact on treatment outcome. The sponsor will capture these life events using the LEC-5 measure. Such events will be entered as Comments in the eCRF and if appropriate, described in the Case Study Report for data outliers, if any.

10.3 Pregnancy

10.3.1 Definition of Able to Become Pregnant

Participants in the following categories are considered a person able to become pregnant (PABP), i.e., fertile:

- 1. Following menarche
- 2. From the time of menarche until becoming postmenopausal unless permanently sterile (see below)
 - A postmenopausal state is defined as no menses for 12 months without an alternative medical cause.
 - PABP on HRT and whose menopausal status is in doubt will be required to use one of the non-estrogen hormonal highly effective contraception methods if they wish to continue their HRT during the study. Otherwise, they must discontinue HRT to allow confirmation of postmenopausal status before study enrollment.
 - Permanent sterilization methods (for the purpose of this study) include:
 - Documented hysterectomy
 - o Documented bilateral salpingectomy
 - o Documented non-surgical hysteroscopic sterilization (Essure)
 - o Documented bilateral oophorectomy
 - o For individuals with permanent infertility due to an alternate medical cause other than the above, (e.g., Mullerian agenesis, androgen insensitivity, gonadal dysgenesis), investigator discretion should be applied to determining study entry.

Note: Documentation can come from the site personnel's review of the participant's medical records, medical examination, or medical history interview.

If fertility is unclear (e.g., amenorrhea in adolescents or athletes) and a menstrual cycle cannot be confirmed before first dose of study intervention, additional evaluation should be considered.

10.3.2 Contraception Guidelines

Study participants who were assigned male at birth with partners able to become pregnant will not be required to practice contraception. Adequate contraceptive methods are required for participants able to become pregnant and include:

- Intrauterine device (IUD)
- Intrauterine hormone-releasing system (IUS)
- Non-oral hormonal methods, including injected, intravaginal, implanted, transdermal
- Oral hormones plus a barrier contraception (condom, diaphragm, or spermicide)
- Double barrier method (at least two of the following: condom, diaphragm, and spermicide)
- Vasectomized sole partner

- Abstinence from penile-vaginal intercourse
 - The reliability of abstinence should be evaluated carefully with the participant in relation to their general lifestyle. An additional acceptable contraceptive method should be discussed with the participant in case they decide to engage in penile-vaginal intercourse during the course of the study.

For questions about acceptable contraceptive methods, contact the Medical Monitor.

10.3.3 Follow-up Requirements

Details of all pregnancies in study participants and their partners will be collected after Enrollment (Visit 0) and collected through 10 days after the last Experimental Session. Pregnancies should be reported to the sponsor via telephone or email within 24 hours of site staff awareness.

In the event of a pregnancy, the participant will discontinue Experimental Sessions but may continue with non-drug Integrative Sessions, PCL-5 assessments, and Study Termination procedures. At a minimum, prior to withdrawal from the study, efforts should be made to assess the final PCL-5 immediately and complete Study Termination procedures.

The investigator will collect follow-up information on the participant or their partner and neonate and forward to the sponsor until the outcome of the pregnancy, which will be reported on an optional Pregnancy eCRF. Any termination, elective or spontaneous, will be reported. Abnormal pregnancy outcomes, such as spontaneous abortion, fetal death, stillbirth, congenital abnormalities, or ectopic pregnancy, will be reported as SAEs.

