9:55	Baseline BP, body temperature, pulse
10:00	IMP Administration
11:30	BP, body temperature, pulse
	Supplemental Dose Administration, unless tolerability issues emerge with the
	first dose, or it is refused by the participant.
17:30	C-SSRS, BP, body temperature, pulse

Pre-IMP administration

In the hours before IMP administration, the following procedures will take place:

- 24 to 48 hours prior to each Experimental Session, the site team will obtain the container assignment.
- On the day of the Experimental Session, the participant will arrive approximately 30 to 60 minutes prior to IMP administration.
- The site team will ensure the participant has not used caffeine or nicotine 2 hours prior and has fasted and not used cannabis or alcohol since 12:00 AM (midnight) prior to IMP administration and complied with all other requirements per Section 3.3 Lifestyle Modifications.
- The site team will inquire about any possible changes in health to ensure the participant continues to meet all eligibility requirements and record AEs as described in Section 10.0 Safety.
- The site team will instruct the participant that they will not be able to use caffeine or nicotine at least 6 hours after the IMP administration.
- The site team will complete urine drug screen, pregnancy test, and concomitant medication review.
 - A positive drug screen will be reviewed by the site physician and may be cause for delaying IMP administration to a later time, rescheduling the session to a later date, or withdrawing the participant from the study, based on Medical Monitor review.
 - A positive pregnancy test that has been confirmed is cause for withdrawal from the protocol.
- The therapy pair will administer Since Last Visit C-SSRS.
- The therapy pair will review procedures for the Experimental Session with the participant and discuss the participant's goals, intentions, and concerns and some of the commonly experienced effects of MDMA. The choice of whether to keep the dose the same or change it from the first Experimental Session will be made by the therapy pair in consultation with the site physician based on observed response, tolerability to the previously administered dose, and discussion with the participant.
- If the participant continues to be eligible, the session will proceed.

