7.4 Study Termination

Study Termination (Visit 16) will take place 24 to 32 days after the Experimental Session 3 (Visit 12) and after the last Integrative Session 3.3 (Visit 15). Participants who have withdrawn from treatment but have continued for follow-up will also complete this assessment immediately upon withdrawal.

The site team will:

- Inquire about any possible changes in health. Assess the participant's mental health and the status of any previously recorded AEs. Record AEs as described in Section 10.0 Safety.
- Inquire about concomitant medication use and adherence.
- Administer Since Last Visit C-SSRS.
- Measure weight (used to calculate BMI).
- Measure blood pressure.
- Perform urine pregnancy test for participants who are able to become pregnant.
- Provide and discuss a study Exit Plan/Plan for Moving Forward.
- Ask them to enroll into the LTFU extension study with a visit at least 6 months after the last Experimental Session. Review contact information and Informed Consent procedures for LTFU.
- Actively support participant in completion of Study Termination self-reported measures. Completion of the measures does not need to be recorded.
 - o LEC-5
 - o PCL-5, under the direction of the therapy pair, who will remind them of the index trauma listed in the parent study to which PTSD symptoms should be anchored
 - o SDS
 - o BDI-II
 - o CPGS
 - o EQ-5D-5L
 - AUDIT
 - o DUDIT
 - SRNUEAT-26
 - HPOSF

After all Study Termination measures and assessments are completed, the participant is considered terminated from the study. The participant can resume normal everyday life.

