Reproductive and Developmental Risks	MDMA has been demonstrated to be negative for genotoxicity, both in vitro and in vivo , with and without metabolic activation. While there are no clinical data on the use of MDMA in pregnant individuals, repeated dose toxicity studies of adequate duration, fertility, early embryonic development, and embryofetal development studies of MDMA in rats and rabbits have not found direct or indirect harmful effects with respect to reproductive toxicity, see IB.	 Participants who are pregnant will be excluded from participation. Urine pregnancy tests will be conducted during screening and immediately prior to any experimental session. Any positive urine pregnancy test may be followed by a confirmatory serum analysis. A final urine pregnancy test will be conducted after the end of systemic exposure. Participants who are able to become pregnant will be required to adhere to contraceptive measures with a <1% failure rate, as described in Section 10.3.2 Contraception Guidelines. Information on all pregnancies in participants and their partners will be collected after the start of study intervention and until the participant's final visit. Pregnancies will be followed until the outcome of the pregnancy is known. Live births will be followed for 30 days after delivery.
Abuse Potential	Because the medication is considered a controlled substance in the U.S. with known abuse potential, the FDA has requested that patients are consistently monitored for adverse events that could be suggestive of abuse potential among research participants treated with MDMA.	 Participants with current severe alcohol and/or substance use disorders which could pose a safety concern or interfere with the therapeutic process will not be eligible for the study, see Section 3.2 Exclusion Criteria. MDMA is only administered under the supervision of the clinical investigator and no takehome doses are administered. MDMA administration and handling follows all regulations pertaining to the use of controlled substances within research studies. Use of alcohol and other recreational drugs will be monitored in the study. Behavior suggestive of abuse potential will be recorded as an AESI and reported in the same manner as an SAE, refer to Section 10.1.3 Adverse Events of Special Interest (AESI).

Risk of Other Stu	dy Procedures	

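### The protocol gives two incompatible pregnancy-collection windows; for participants who complete Session 3, the Visit 16 pregnancy test falls 14 to 22 days after one of them has closed

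*Protocol*

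**What the plan says.** Three places in the protocol define when pregnancies in participants and their partners are collected.

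- Section 10.3.3: details are "collected after Enrollment (Visit 0) and collected through 10 days after the last Experimental Session".
- Section 10.1.6: details "will be collected after the start of study intervention and until the participant's final visit".
- Section 9.1, Table 9, reproductive risk row: "Information on all pregnancies in participants and their partners will be collected after the start of study intervention and until the participant's final visit".

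Tests are scheduled at Screening, at Visit 3, before dosing at Visits 4, 8 and 12, and at Visit 16 (Protocol Table 5 and Sections 7.1.3, 7.2.2, 7.3.1 and 7.4). For Visit 16, Section 7.4 tells the site team: "Perform urine pregnancy test for participants who are able to become pregnant". Table 9 gives the purpose: "A final urine pregnancy test will be conducted after the end of systemic exposure". Section 7.4 places Visit 16 on day 24 to 32 after Session 3. The SAP's own schedule (Section 5.0, Table 2) ticks the pregnancy row at Visits 4, 8 and 12 of the treatment part and leaves Visit 16 blank.

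Four places say what happens to a pregnant participant.

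- Section 7.3.1, on the pre-session test: "A positive pregnancy test that has been confirmed is cause for withdrawal" from the protocol.
- Section 4.4.4: where safety is judged to be affected, dosing stops but the participant stays for the related Integrative Sessions.
- Section 10.3.3: "the participant will discontinue Experimental Sessions but may continue with non-drug Integrative Sessions", and also with PCL-5 assessments and termination procedures. No approval is mentioned.
- Section 10.1.6: non-drug sessions may continue only in some cases. The sponsor and the ethics board must first approve in writing, signed consent must be given, and the investigator must agree to monitor the outcome.

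**The concern.** The collection rules are operative safety-reporting instructions in the current text, and they cannot all be followed as written. The end date matters most. The protocol schedules a test specifically to look for pregnancy after exposure has ended, yet one of its three statements of the window has closed before that test is done.

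The case at risk is a conception close to the last dose that is too early to show on the pre-session urine test and is first seen at Visit 16. Section 3.1 recognises that an early pregnancy can go undetected at entry, and Table 9 states that there are no clinical data on MDMA in pregnancy. Each exposed pregnancy is therefore information the study means to capture and follow.

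The disposition rules are a second, separate conflict. One event leads to different outcomes and different approval steps depending on the section consulted, which also affects whether that participant's later PCL-5 scores are collected.

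**Working it through.** The plan states no figure for this point, so there is none to reproduce. The check is day arithmetic and a comparison of sections.

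**Inputs**

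- Close of the 10.3.3 window: day 10 after the last session.
- Visit 16: day 24 to 32 after Session 3 (Section 7.4).
- Interval between sessions: 21 to 56 days (Section 7.3.1).
- MDMA half-life: 7 to 9 hours (Section 1.2.2).
- Contraception after the last dose: at least 10 days (Section 3.1, criterion 9).

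**Step 1. Visit 16 test against the 10.3.3 window**

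Gap = Visit 16 day − 10.

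- Earliest: 24 − 10 = 14 days.
- Latest: 32 − 10 = 22 days.

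This holds for participants who complete Session 3. Under Section 7.4, those who withdraw from treatment but stay in follow-up have the termination assessment at once, which may fall within 10 days of their last session.

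**Step 2. Each scheduled test against both windows**

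Two readings are assumed here: the 10 days limit detection, and study intervention starts with the first dose. The protocol states neither.

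| Test | 10.3.3 | 10.1.6 and Table 9 |
|---|---|---|
| Screening | outside | outside |
| Visit 3; Visit 4 pre-dose | inside | outside |
| Visits 8 and 12 pre-dose | depends on the meaning of last session | inside |
| Visit 16, completers | outside by 14 to 22 days | inside |

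In the third row, a confirmed positive stops that session. If the last session means the last one actually held, it took place 21 to 56 days earlier, and the test is 21 − 10 = 11 to 56 − 10 = 46 days past the cutoff.

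**Step 3. Which pregnancies could be exposed ones**

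Take five half-lives as the end of exposure. This is an assumption; the protocol uses the same multiple for medication washout.

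- 5 × 7 = 35 hours, and 35 / 24 ≈ 1.5 days.
- 5 × 9 = 45 hours, and 45 / 24 ≈ 1.9 days.

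A conception after day 10 is then not an exposed one. A conception at or before the last dose, or within about two days of it, can be, and Visit 16 may be the first scheduled test to show it.

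**Step 4. Disposition, side by side**

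| Section | Stays in the study? | Prior approval required? |
|---|---|---|
| 7.3.1 | cause for withdrawal | not stated |
| 4.4.4 | yes, for related Integrative Sessions | not stated |
| 10.3.3 | may continue | not stated |
| 10.1.6 | in some cases | sponsor, ethics board and signed consent |

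**The case against.** The strongest reply is that nothing need be lost. Read together, the three statements cover Visit 0 to the last visit. Sections 10.1.6 and 10.3.3 and Table 9 all require follow-up to the outcome of the pregnancy, and that duty has no day limit. The 10 days in 10.3.3 match the contraception period, so they may have been meant as a limit on conception, in which case an exposed pregnancy first found at Visit 16 is inside the window. Telephone contacts every other day for 14 days (Section 7.3.2) also ask about health changes across the whole 10 days.

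Most of this stands, and it makes the consequence conditional. It does not remove the contradiction. Section 10.3.3 speaks of collection and never mentions conception, so a site would have to guess the intent, and no text says the sections are to be combined.

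Four stronger readings are tempting and are not supported.

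- A reader might infer that Visit 16 is the sole pregnancy test after any dosing. It is not: Visits 8 and 12 test after earlier doses. It is the only scheduled test after the last dose.
- A reader might infer that exposed pregnancies will go unfollowed. That needs a site to use 10.3.3 alone and to read the 10 days as a detection limit.
- A reader might express the gap as a share of follow-up time after the last dose. That would be calendar time, not exposed pregnancies, as Step 3 shows.
- A reader might infer that withdrawal under 7.3.1 ends pregnancy follow-up. It does not say so, and neither 10.1.6 nor 10.3.3 makes outcome follow-up depend on staying in the study.

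**Conclusion.** The contradiction is real and can be read directly from the current text: two windows that differ at the start and at the end, with 10.1.6 and Table 9 on one side and 10.3.3 on the other. For participants who complete Session 3, the Visit 16 test comes 14 to 22 days after the 10.3.3 window has closed.

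The harm is narrower than the gap. It concerns a pregnancy conceived near the last dose, first detected at Visit 16, at a site that follows 10.3.3 alone on the detection reading. The documents give no pregnancy rate, so the number of such cases cannot be estimated. The difference at the start of the window concerns pregnancies before any dose in this study, so it is a matter of consistency rather than of exposure.

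The blank Visit 16 cell in the SAP schedule is a further mismatch with the protocol, and the disposition rules conflict independently of the window. Sample size and alpha are not touched. This is a safety-reporting inconsistency that should be corrected.

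**What to change.** - Reconcile Protocol Sections 9.1 (Table 9), 10.1.6 and 10.3.3 into one reporting window. It needs one defined start and one end that takes in the result of the Visit 16 test already scheduled. It should also say whether it refers to the date of conception or the date of detection, and what the last session means for a participant who stops early.
- Align the pregnancy row of SAP Table 2 with Protocol Table 5 and Section 7.4.
- Reconcile Sections 4.4.4, 7.3.1, 10.1.6 and 10.3.3 on what follows a positive test and which approvals apply. Which disposition is right is a clinical and regulatory decision on which this review takes no position.

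The cost is wording in the protocol and one cell in the SAP schedule. The tests and the pregnancy form already exist, and no new visit, procedure or analysis is needed.
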